3.2.6. Drug-Drug Interactions

As detailed in Section 3.2.4, more than one enzymatic pathway is involved in the metabolism of PHA-848125AC, decreasing the risk for unwanted clinical relevant drug-drug interactions. Also, PHA-848125 did not activate human and mouse PXR, suggesting that the compound is unlikely to increase the CYP3A mediated enzyme activities by increasing its gene transcription.

Significant drug-drug-interactions are therefore not expected.

3.2.7. Phase I clinical trials

The phase I clinical program of PHA-848125AC as a single agent is ongoing with three studies testing four different schedules (daily x 7 every 2 weeks; 4 days on / 3 days off x 3 weeks every 4 weeks; daily x 21 days every 4 weeks; daily x 14 days every 3 weeks), being conducted in US and Europe. Both a flat dose approach and a BSA-based approach have been investigated.

The clinical experience gained so far (July 2009) on overall 90 patients treated for 277 cycles indicated that the safety profile of the compound is characterized by a dose-limiting neurological toxicity and, to a lesser extent, by gastrointestinal toxicity. Nausea and/or vomiting and /or diarrhea were mostly of grade 1- 2 in severity and were manageable with appropriate therapy, including hydration. Haematological toxicity, mainly represented by neutrophils decrease, was reported in some patients only. A prolonged transaminitis was occasionally observed with the 7 days on / 7 days off schedule, however, with a treatment

Tiziana Life Sciences, PLC - Confidential Page 30 of 101

Milciclib maleate (PHA-848125AC)	CDKO-125a-006-P4
Protocol for Study CDKO-125a-006	09 March 2017

3.2.8. Pharmacokinetics in Humans

The pharmacokinetics of PHA-848125AC and its major metabolite, NMS-867734 (M1), has been investigated in the three ongoing phase I clinical trials CDKO-125a-001, CDKO-125a-Tiziana Life Sciences, PLC - Confidential Page 31 of 101 002, CDKO-125a-003. Results for PHA-848125AC are summarized in Table 1, Table 2 and Table 3, respectively.

In particular, in the CDKO-125a-001 study, first schedule, which is the same schedule adopted in the present study, the pharmacokinetic profile of PHA-848125AC was characterized by:

- achievement of maximal plasma concentration at 2 4 hours post dosing, after single and repeated administration
- terminal half-life in the range of 30 and 40 hours
- good dose proportionality in systemic exposure, in the range of 50-300 mg/day
- similar exposure to the compound after subsequent cycles of treatment
- inter-patient variability limited
- AUC of the major metabolite lower than that of the parent compound, accounting for 30-50%. Its half-life is comparable to or slightly longer than that of the parent compound.

Of note, at the RP2D of 150 mg/day, which is the dose to be administered to patients in the present study:

- on day 1 in cycle 1, maximal plasma concentration was 0.66±0.24 μM (n=6), attained on average at 2.5 h post-dosing. The corresponding daily AUC was 8.86±2.64 μM·h (n=6).
- after seven days of treatment in cycle 1, maximal plasma concentration was 1.47 ± 0.51 μ M (n=6), attained on average at 2.5 h post-dosing and corresponding to a daily AUC of $25.31\pm8.56 \mu$ M·h (n=6).
- the day 7/day 1 AUC_(0-24h) ratio was around 3, in line with what was expected considering the schedule and the half-life of the compound that at this dose level was on average 33.3 hours.

Overall, at similar doses administered with different schedules, comparable PHA-848125AC PK profile was observed across studies.

For more details on PHA-848125AC, please refer to Investigator Brochure for PHA 848125AC, Version 7, 2011 [23].

Tiziana Life Sciences, PLC - Confidential Page 32 of 101

CDKO-125a-001 first schedule (7 days on, 7 days off q2wks)						
Day	Dose (mg/day)	No. of Pts	Cmax (µM)	AUC0-t(24h) (μM· h)	tmax (h)	t1/2,λz (h)
1	50	3	0.2±0.06	2.56±0.52	3.35±1.17	N/A
7	50	3	0.4±0.15	6.84±2.21	3.33±1.15	32.8±12.2
1	100	6	0.44 ± 0.07	6.19±2.26	3.5±2.51	N/A
7	100	6	1.2±0.47	19.9±10.5	2.76±1.89	38.2±9.28
1	150	6	0.66±0.24	8.86±2.64	2.5±1.22	N/A
7	150	6	1.47±0.51	25.3±8.54	2.5±1.22	33.3±7.08
1	200	6	0.56±0.11	8.41±1.68	4±1.26	N/A
7	200	6	1.68±0.17	29.2±4.5	4.33±1.51	31.8±4.68
1	300	1	1.15	22.3	2	N/A
7	300	1	5.12	83.6	4	31.3
	CDKO-	125a-001	second schedule (4 days on, 3 days o	off x 3wks q4wks)	1
Day	Dose (mg/day)	No. of Pts	Cmax (uM)	AUC0-t(24h) (uM·h)	tmax (h)	t1/2,λz (h)
1	150	3	0.42±0.1	6.67±1.72	4±0	N/A
18	150	3	$1.08{\pm}0.07$	19.5±4.27	3.13±1.96	41±3.01
1	180	1	0.55	6.67±1.72	2	N/A
18	180	1	1.22 (Day 4)	6.67±1.72	4	
1	200	4	0.79±0.5	9.58±7.34	2±0	N/A
18	200	3	2.33±0.58	33.3±2.56	1.71±0.44	25.9±8.38
N/A: not applicable						

Table 1. PHA-848125AC pharmacokinetic data from CDKO-125a-001 study

Table 2. PHA-848125AC pharmacokinetic data from CDKO-125a-002 study

CDKO-125a-002 (14 days on, 7 days off q3wks)						
Day	Dose (mg/m²/day)	No. of Pts	Cmax (µM)	AUC0-t(24h) (μM· h)	tmax (h)	t1/2,λz (h)
1	18	5	0.103 ± 0.042	1.7±0.487	4.8±1.09	N/A
14	18	4	0.248 ± 0.064	4.08±1.23	2.5±1	40.1±6.68
N/A: not applicable						

Tiziana Life Sciences, PLC - Confidential Page 33 of 101

CDKO-125a-003 first schedule (21 days on, 7 days off q4wks)						
Day	Dose	No. of	Cmax	AUC0-t(24h)	tmax (h)	t1/2,λz
	(mg/m²/day)	Pts	(µM)	(µM∙ h)		(h)
1	16	7	0.22 ± 0.28	2.54±2.92	2.86±1.57	N/A
21	16	6	0.25 ± 0.08	4.07±1.29	2.96±1.15	33.6±10
1	24	6	0.2±0.09	2.48±0.92	1.78±1.26	N/A
21	24	5	0.42 ± 0.2	6.24±2.44	2.43±2.05	37.1±5.77
	CDK	O-125a-0	003 second schedu	le (14 days on, 7 d	ays off q3wks)	
Day	Dose	No. of	Cmax	AUC0-t(24h)	tmax (h)	t1/2,λz
	(mg/m ² /day)	Pts	(µM)	(µM∙ h)		(h)
1	24	3	$0.18{\pm}0.05$	2.32±0.54	2.3±1.5	N/A
14	24	3	0.45±0.22	7.1±3.94	1.7±0.6	41.2±4.26
1	48	3	0.31±0.09	4.5±1.43	2.8±1.4	N/A
14	48	3	0.7±0.44	1.27±7.9	3.3±1.2	28.9±1.6
N/A: not applicable						

Table 3. PHA-848125AC pharmacokinetic data from CDKO-125a-003 study

3.3. Rationale for the use of PHA-848125AC in Thymic Carcinoma

Chemotherapy was shown to have significant antitumor activity against unresectable, recurrent or metastatic thymomas and thymic carcinomas, but an optimal treatment strategy has not been determined and other drugs are needed to improve the outcome of patients with advanced invasive tumors [10].

In recent years, a few studies on molecular changes in thymomas point to alterations that may be of use in selecting patients for targeted therapies [4-8]. Unfortunately for some of them, such as KIT and EGFR inhibitors, the reported results seem to be discouraging [12-14]. In addition, despite a lack of correlation of thymidilate synthase expression with thymoma clinicopathological characteristics, pemetrexed obtained interesting responses in stage IVA thymomas, but not in thymic carcinomas [20].

The pyrazoloquinazoline PHA-848125 is a compound counteracting the effects of some of the other so far identified, but not yet exploited, molecular alterations found in thymoma and thymic carcinoma, e.g. underexpressed p21 and p27 and overexpressed TRKA [7,8]. These targets are not yet been investigated in therapeutic intent clinical trials.

In fact, p21 and p27 encode natural potent cyclin-dependent kinase inhibitors and their ablation in the cancer cell results in an activation of cyclin E/CDK2 or cyclin D/CDK4 complexes and thus in uncontrolled cell cycle progression and cell proliferation [24-32], while TRKA activation promotes tumor growth [33], probably through MAPK pathway activation. PHA-848125 potently inhibits both the CDK/Cyclin complexes and TRKA,

Tiziana Life Sciences, PLC - Confidential Page 34 of 101 proposing in this way to be a "selective dual inhibitor" and appearing particularly attractive in this disease.

The preliminary results in early clinical trials on thymic carcinomas patients (2 out of 3 patients with clinical benefit) support the hypothesis that PHA-848125 could be of therapeutic value for patients with this tumor type.

An exploratory analysis on the relationship of molecular features of p53 (natural regulator of p21), p21, p27, cyclin D1, p75, TRKA and other genes/proteins involved in the PHA-848125AC mechanism of action with treatment efficacy variables will be possibly performed in tumor biopsies of consenting patients obtained before study entry.

4. TRIAL OBJECTIVES AND ENDPOINTS

4.1. Objectives

4.1.1. Primary Objective

• Assessment of the antitumor activity of PHA-848125AC as second-line treatment in patients with recurrent or metastatic, unresectable thymic carcinoma previously treated with chemotherapy. Antitumor activity will be evaluated on the basis of the progression-free survival status at 3 months.

4.1.2. Secondary Objectives

- Assessment of additional measures of tumor control to further characterize the efficacy profile of PHA-848125AC in recurrent or metastatic, unresectable thymic carcinoma previously treated with chemotherapy.
- Evaluation of the safety profile of repeated administrations of PHA-848125AC in patients with recurrent or metastatic, unresectable thymic carcinoma previously treated with chemotherapy.

4.1.3. Exploratory Objective

• Relationship of baseline molecular features in tumor biopsies of p53, p21, p27, cyclin D1, p75, TRKA and other genes/proteins involved in the PHA-848125AC mechanism of action with treatment efficacy.

4.2. Endpoints

4.2.1. Primary Endpoint

• Progression-free survival rate at 3 months (PFS-3 rate). The PFS-3 rate, will be calculated as the proportion of evaluable patients (see Section 12.2) known to be alive

and progression-free at \geq 3 months since study treatment start out of the total number of evaluable patients.

4.2.2. Secondary Endpoints

- Confirmed Objective Response Rate (CR + PR) according to RECIST guideline (version 1.1).
- Disease Control Rate (Confirmed Objective Response Rate $+ \ge 6$ weeks SD rate).
- Progression-free survival, calculated as the time from the date of treatment start to the date of first documentation of objective progression or of death due to any cause, whichever comes first.
- Duration of Response, measured from the time measurement criteria are first met for CR/PR (whichever is first recorded) until the first date that recurrent or progressive disease is objectively documented (taking as reference for progressive disease the smallest measurements recorded on study).
- Overall Survival (OS), i.e. the time from the date of treatment start to the date of death from any cause.
- Overall safety profile, evaluated on the basis of laboratory and clinical safety parameters (i.e. hematology and blood chemistry, urinalysis, vital signs, ophthalmologic examinations and adverse events emerging during the trial). The National Cancer Institute Common Terminology Criteria for Adverse Events (NCI CTCAE) Version 3.0 will be used for the severity grading of adverse events and of hematological and blood chemistry abnormalities.

4.2.3. Exploratory Endpoint

• Baseline characterization of selected biomarkers (p53, p21, p27, cyclin D1, p75, TRKA and other genes/proteins involved in the PHA-848125AC mechanism of action) in tumor tissue of consenting patients. Assessments will be done on paraffin embedded blocks, obtained from all patients before study entry, by IHC and other possible techniques, such as FISH and PCR.

5. TRIAL DESIGN AND DESIGN RATIONALE

In consideration of the exploratory nature of the study, the Simon's optimal 2 stage design is adopted for this single-arm, open-label, multicentre phase II clinical trial of PHA-848125AC administered to patients with recurrent or metastatic, unresectable thymic carcinoma previously treated with chemotherapy (only one prior systemic therapy allowed).

The intent of the study is to assess the antitumor activity of PHA-848125AC and ultimately to improve the outcome of patients with thymic carcinoma who have already exploited one chemotherapy option. To this purpose, the progression free survival rate at 3 months is considered to be an appropriate primary endpoint.

Tiziana Life Sciences, PLC - Confidential Page 36 of 101
Milciclib maleate (PHA-848125AC)	CDKO-125a-006-P4
Protocol for Study CDKO-125a-006	09 March 2017

Patients will receive repeated cycles of PHA-848125AC administered orally once daily at the flat dose of 150 mg/day, according to a 7 days on / 7 days off schedule in 2-week cycles. A treatment cycle will therefore comprise 7 days of PHA-848125AC administration (Days 1 to 7) followed by 7 days of rest (Days 8 to 14) for a total of a 14 days period (2-week cycle).

The 150 mg/day dose has been selected based on the results of the first single agent Phase I study in solid tumor patients (CDKO-125a-001), where PHA-848125AC was administered with the same schedule, at escalating dose levels, ranging from 50 to 300 mg/day: the dose of 150 mg/day was assessed as the dose recommended for Phase II investigations (RP2D); this dose was associated with mild/moderate reversible adverse events, mostly represented by maximum grade 2 nausea and/or vomiting and/or diarrhea and maximum grade 2 neurological effects.

Patients may continue on study treatment until disease progression, patient refusal or withdrawal of patient consent, or the occurrence of unacceptable toxicity and will be followed up for survival up to the end of the study and in any case for no more than 2 years from the end of treatment.

Patients remaining on treatment longer than 6 cycles of treatment are allowed to come back to the site once every 3 cycles (once every 1.5 month) for safety evaluation, drug dispensing, oncologic assessment and ocular examination. At the end of each cycle instead of the site visit the patient is required to perform the laboratory tests locally. Also a phone interview will be performed by the Investigator to clarify the toxicity experienced by the patient during the observation period. The Investigator must document in writing the results of the phone call with the patient in the medical chart. Data are to be reported in the CRF. Only after evaluation of the laboratories' results and of the patient's safety performed by phone, the Investigator deems necessary to physically visit the patient (especially for the evaluation of his/her neurological status) or he has any doubt about the capability of the self-evaluation for a specific patient, it is left to the Investigator's discretion the possibility to require that the patient reaches the site before continuing the treatment.

A cut-off date is planned on 31 May 2017 in order to proceed with clinical database closure and preparation of the clinical study report.

The management of patients after the cut-off date of 31 May 2017 should be conducted as per Section 9.5.

The total number of evaluable patients for the primary efficacy analysis ranges from 17 (if the trial stops at the end of the 1st stage) to 54 (if the trial proceeds up to the completion of the 2nd stage). Accounting for a 10%-15% proportion of non evaluable patients, up to 20 patients could be required in the 1st stage of the study and up to 60 patients could be required for completing the trial (1st and 2nd stage).

Tiziana Life Sciences, PLC - Confidential Page 37 of 101 For statistical considerations, see Section 12.

5.1. Confirmation of histological diagnosis

Histological confirmation of thymic carcinoma for all patients will be obtained by an Independent Review Committee during the course of the study, based on paraffin embedded tumor tissue slides retrieved from the patients.

6. SUBJECT SELECTION

This clinical trial can fulfill its objectives only if appropriate subjects are enrolled. The following eligibility criteria are designed to select subjects for whom protocol treatment is considered appropriate. All relevant medical and non-medical conditions should be taken into consideration when deciding whether this protocol is suitable for a particular subject. Eligibility criteria may not be waived by the investigator and are subject to review in the case of a Good Clinical Practices (GCP) or a regulatory authority audit. Any questions regarding a subject's eligibility should be discussed with NMS Study Management prior to enrollment.

6.1. Subject Inclusion Criteria

Subjects must meet all of the following inclusion criteria to be eligible for enrollment into the study:

- 1. Signed and dated IRB/IEC-approved Informed Consent.
- 2. Histologically or cytologically proven diagnosis of unresectable B3 thymoma or thymic carcinoma recurrent or progressing after prior chemotherapy (only one prior systemic therapy allowed).
- 3. Presence of measurable disease defined as at least one lesion that can be accurately measured by CT scan in at least one dimension, as > 10 mm for non nodal lesions (longest diameter to be recorded) and ≥ 15 mm for lymph nodal lesions (short axis to be recorded). (CT scan is the desirable method for lesion measurement. Other measurement techniques [eg MRI] are acceptable [but not for lung lesions] provided that the size of the measurable lesion is twice the slice thickness of the MRI). Tumor lesions situated in a previously irradiated area, or in an area subjected to other loco-regional therapy, are usually not considered measurable unless there has been demonstrated progression in the lesion.
- 4. Age \geq 18 years.
- 5. ECOG performance status 0-1.
- 6. Estimated life expectancy of at least 3 months.
- 7. Negative pregnancy test (if female in reproductive years).

Tiziana Life Sciences, PLC - Confidential Page 38 of 101

Milciclib maleate (PHA-848125AC)	CDKO-125a-006-P4
Protocol for Study CDKO-125a-006	09 March 2017

- 8. Agreement upon the use of effective contraceptive methods (hormonal or barrier method of birth control, or abstinence) prior to study entry and for the duration of study participation, if men and women of child producing potential.
- 9. Adequate liver function:

•	Total S	erum B	ilirubin	\leq 1.5 x upper limit of normal (ULN)
	æ			

- Transaminases (AST/ALT) ≤ 2.5 ULN (if liver metastases are present, then ≤ 5 ULN is allowed)
- ALP ≤ 2.5 ULN (if liver and/or bone metastases are present, then ≤ 5 ULN is allowed).

10. Adequate renal function:

• Serum Creatinine ≤ ULN or

Creatinine Clearance calculated by Cockcroft and Gault's formula > 60 mL/min.

- 11. Adequate hematologic status:
 - ANC $\geq 1,500 \text{ cells/mm}^3$
 - Platelet Count $\geq 100,000 \text{ cells/mm}^3$
 - Hemoglobin $\geq 9.0 \text{ g/dL}.$
- 12. At the time of start of treatment, at least 2 weeks must have elapsed since completion of prior chemotherapy, minor surgery, radiotherapy (provided that no more than 25% of bone marrow reserve has been irradiated).
- 13. With the exception of alopecia, resolution of all acute toxic effects of any prior chemotherapy, surgery or radiotherapy to NCI CTC (Version 3.0) grade ≤ 1 and to the baseline laboratory values as defined in Inclusion Criteria Number 9, 10, 11.
- 14. Able and willing to comply with scheduled visits, therapy plans, and laboratory tests required in this protocol.
- 15. Capability to swallow capsules intact (without chewing, crushing, or opening).

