The loss of control of cell cycle checkpoints seems a common occurrence in thymomas, supporting the idea that functional cooperation between different cell cycle inhibitor proteins regulates cell growth control and tumor suppression. Univariate analyses on the expression of p21 and p27 in specimens from 25 encapsulated thymomas (using immunohistochemistry) suggest that negative expressions of p21 and p27 (natural inhibitors of CDKs) significantly correlates with poor prognosis for disease-free survival [7]. In addition, some members of the neurotrophin receptors family seem to play a significant role in this disease: in a study investigating the expression of neurotrophin receptors in thymic epithelial tumors on a quite large series of patients (N=99) [8], the pattern of TRKA expression was analyzed according to WHO classification for the histologic subtypes (A, AB, B1, B2, B3, C). All patients, except one, had immunostaining for TRKA expression in the tumors gradually increasing from type A to C. Conversely, none of the tumors showed TRKB or TRKC immunoreactivity. In addition, from type A to type C, there was a decreasing percentage of tumors with p75 immunostaining. These observations suggest a further elucidation on the specific role of TRKA and p75 in this disease.

Tiziana Life Sciences, PLC - Confidential Page 23 of 101

Milciclib maleate (PHA-848125AC)	CDKO-125a-006-P4
Protocol for Study CDKO-125a-006	09 March 2017

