In a single agent study with pemetrexed, on 23 previously treated evaluable patients with unresectable stage IV A and B disease, there were 4 objective responses (2 CRs and 2 PRs) (17% RR). Responses were obtained only in stage IVA thymoma patients, with a median duration of time to progression of 45.4 weeks; in thymic carcinoma patients the median duration of time to progression was much shorter (5.1 weeks) [20]. In other two recent series of previously treated patients with thymic malignancies, objective responses were reported in B2 and B2/3 tumors (no type C thymic carcinoma patients were enrolled in the first study) with a gencitabine/ capecitabine combination [21] and with the histone deacetylase inhibitor (HDAC) belinostat [22]. Also in this second study, responses were obtained only in thymoma patients and no responses were seen in the 8 evaluable patients with thymic carcinoma. Thymic carcinoma is therefore confirmed as a type of cancer where prognosis is particularly poor and the course of the disease more aggressive compared to the other thymomas.

Tiziana Life Sciences, PLC - Confidential Page 24 of 101 Given the current clinical scenario, in thymic carcinoma patients previously treated with chemotherapy, a single agent therapy is able to induce a median PFS of approximately 5.1 weeks [20], roughly corresponding to an estimated PFS rate at 3 months of about 17%. Therefore a 33% target PFS-rate at three months could be regarded as clinically interesting for a new investigational agent.

3.2. РНА-848125АС

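### Inclusion criterion 2 admits B3 thymoma, but the objective, benchmark, histology review and evaluable set cover thymic carcinoma only, so a confirmed B3 patient is treated but never evaluable

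*Protocol*

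**What the plan says.** **Entry.** Criterion 2, worded identically in the Synopsis and in Section 6.1, requires "Histologically or cytologically proven diagnosis of unresectable B3 thymoma or thymic carcinoma recurrent or progressing after prior chemotherapy".

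**Objective and design.** Section 4.1.1 sets the question in patients with "recurrent or metastatic, unresectable thymic carcinoma previously treated with chemotherapy". Section 5 describes the trial population as recurrent or metastatic "unresectable thymic carcinoma previously treated with chemotherapy (only one prior systemic therapy allowed"). Neither mentions B3.

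**Benchmark.** Section 3.1 takes a median PFS of 5.1 weeks in previously treated thymic carcinoma, "roughly corresponding to an estimated PFS rate at 3 months of about 17" per cent, and sets the 33% target against it.

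**Subtypes.** Section 3.1 refers to the "WHO classification for the histologic subtypes (A, AB, B1, B2, B3, C"), and in describing an earlier series says that "no type C thymic carcinoma patients were enrolled in the first study". B3 and C are thus separate entries, and C is the carcinoma.

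**Review and analysis sets.** Sections 5.1 and 11.5.1 have an Independent Review Committee confirm thymic carcinoma for every patient while the study is running. Section 12.2 makes that confirmation a condition of the evaluable set, the denominator of the primary PFS-3 rate. The treated set in Section 12.2 needs only one dose and has no histology condition. Section 12.3.4 calls for efficacy results in both sets.

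**Enrolment.** Section 12.1 allows for 10%-15% non-evaluable patients and gives up to 20 enrolled in stage 1 and up to 60 overall. The allowance is not itemised by cause.

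**The concern.** Eligibility and the evaluable definition do not describe the same patients. No passage says why B3 is admitted, how such patients are to be handled, or whether they fall within the 10%-15% allowance.

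Two things are at stake. First, patients may be exposed to the drug who cannot inform the primary question, and each adds to the enrolment needed once the small reserve is used up. Second, the treated-population PFS-3, PFS, response, disease-control and survival results may combine histologies. Section 3.1 says of thymic carcinoma that "prognosis is particularly poor and the course of the disease more aggressive compared to the other thymomas". A mixed treated-population figure could not be read against 17%/33% or as an effect in thymic carcinoma.

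**Working it through.** **1. Can a B3 patient become evaluable?**

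| Step | Protocol place | Confirmed B3 patient |
|---|---|---|
| Eligible | Synopsis and 6.1, criterion 2 | Yes |
| Treated set | 12.2 | Yes, after one dose |
| Committee confirms thymic carcinoma | 5.1, 11.5.1 | No: 3.1 lists B3 apart from type C |
| Evaluable set | 12.2 | No |
| Counted in 17/54 | 12.1, 12.3.4 | No |
| In treated-set efficacy results | 12.2, 12.3.4 | Yes |

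**2. Does the design stand for carcinoma?** Inputs from Section 12.1: p0 = 0.17, p1 = 0.33, n1 = 17 (stop at 3 or fewer), n = 54 (reject H0 at 14 or more). Exact binomial:

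- Stopping probability at p: P[Bin(17, p) ≤ 3]. At 0.17 this is 0.675. The probability of continuing at 0.33 is 0.863.
- Rejection probability at p: Σ over x = 4 to 17 of P[Bin(17, p) = x] × P[Bin(37, p) ≥ 14 − x]. At 0.17 this is 0.0496; at 0.33 it is 0.806.
- Expected size under p0: 17 + (1 − 0.675) × 37 = 29.0.

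These match the table in Section 12.1. They apply to the evaluable set, which by definition holds only confirmed carcinoma.

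**3. Whose benchmark is the 17%?** Assuming exponential PFS with the 5.1-week carcinoma median and 3 months taken as 13.04 weeks: 0.5^(13.04/5.1) = 0.170. The null rate is the carcinoma figure.

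**4. How much room is there for non-evaluable patients?** Stage 1: 20 − 17 = 3 places (3/20 = 15%). Overall: 60 − 54 = 6 places (6/60 = 10%). They must cover every cause in Section 12.2: histology not confirmed, less than 80% of drug in the first two cycles, and missing tumour assessments. Each confirmed B3 patient takes one place, or adds one enrolment once the places are gone.

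**5. Separate check of the enrolment figures.** Enrolled = evaluable/(1 − d), rounded up:

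| d | Stage 1 | Overall |
|---|---|---|
| 10% | 17/0.90 = 18.9 → 19 | 54/0.90 = 60 |
| 15% | 17/0.85 = 20 | 54/0.85 = 63.5 → 64 |

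The stated 20 is the 15% figure, whereas the stated 60 is the 10% figure. This discrepancy does not depend on B3.

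**6. Timing.** This version is dated 09 March 2017, and Section 5 states: "A cut-off date is planned on 31 May 2017". The interval is 22 + 30 + 31 = 83 days, shorter than the 92 days at which the preferred 3-month assessment window opens.

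**The case against.** The strongest reply is that central review already does the work: only confirmed carcinoma enters the primary analysis, and accrual continues to 54 evaluable patients. That stands. A reader might infer inflated type I error. It would arise if B3 patients were counted; for example, with an assumed 20% B3 share and an assumed B3 PFS-3 rate of 30%, the mixed rate is 0.8 × 0.17 + 0.2 × 0.30 = 0.196 and the chance of rejecting H0 is 0.125. Section 12.2 forbids counting them, so this is not a risk in the plan as written. Nor does a loss of power follow, because 60 is a projection and not a stopping point.

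B3 may also have been admitted to catch borderline local diagnoses that the committee would reclassify as carcinoma. That is plausible, but no passage says so, and it would not help a patient whose B3 diagnosis is confirmed.

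The treated-population results are supportive or descriptive, each has an evaluable-set counterpart, and the protocol does not itself compare them with 17%/33%. All of this stands. A table split by histology may also be specified in a statistical analysis plan that is not shown. Such a plan could not, however, reconcile eligibility with the objective or correct the enrolment figure, both of which the protocol fixes.

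Finally, with 83 days to the cut-off, a change to entry comes late. A patient starting after this version would not reach day 92 by then.

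**Conclusion.** The contradiction is real and unreconciled: a committee-confirmed B3 patient is eligible and treated but never evaluable. The primary test is sound (alpha 0.0496, power 0.806). The consequences are limited to possible extra enrolment and mixed histology in supportive and descriptive treated-population efficacy.

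Neither can be sized. The protocol gives no B3 share and no B3-specific outcome, and Section 3.1 contrasts carcinoma with the other thymomas as a group, so it does not establish a prognosis for B3 itself. A reader might try to bound the distortion by letting all 6 spare places of 60 be B3 with every one a success: 6/60 × (1.00 − 0.17) = 8.3 percentage points. That is not a bound. With 10 of 64 it becomes 10/64 × 0.83 = 13.0 points, and with a B3 rate of zero in 6 of 60 it is 6/60 × (0 − 0.17) = −1.7 points. No figure should be quoted.

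The gap between 60 and 64 is a separate, small arithmetic error. It should not be attributed to B3 entry.

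Severity is minor to moderate. The reading that B3 cannot satisfy the evaluable condition rests on Section 3.1's own separation of B3 from type C.

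**What to change.** - **Reconcile the text.** Bring criterion 2 (Synopsis and 6.1) into line with Sections 4.1.1, 5.1, 11.5.1 and 12.2. Either make eligibility match the objective, or declare committee-confirmed B3 patients a separate descriptive group outside the 17/54.
- **Report by histology.** Present treated-population PFS-3, PFS, objective response, disease control and overall survival by committee-reviewed histology, and read 17%/33% against confirmed thymic carcinoma only.
- **Correct the enrolment figure, as a separate item.** For 10%-15% non-evaluable, state 19-20 in stage 1 and 60-64 overall, and say whether the allowance includes histology failures. If B3 patients are kept as a separate group, state that they come on top.

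The cost is a few sentences in the protocol and one split of existing tables on data already centrally reviewed. The only downside is that any B3 group will be small and purely descriptive. Given the date of this version, the reporting split and the restated figure have the most practical effect.
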